### **Recruitment:**

We recruited 20 sites (14 in Ontario and 6 in British Columbia, Canada). Site recruitment focused primarily on the engagement of contacted sites to reduce the risk of site withdrawl. For patient participant recruitment, staff at each primary care site screened patients for their willingness to participate when they called to book an appointment. If patients booked online, their reason for visit was screened by the clinic staff and staff reached out to potential participants for their willingness to be contacted by a research assistant. Trained research assistants screened potential participants using inclusion/exclusion criteria and enrolled consenting patients. Patients who raised LBP with any provider during a clinical encounter were also identified as potential participants. In these cases, they were directed to the administrative team, who then connected them with a research assistant for screening and enrollment. Balance in recruitment across arms and across clusters was monitored throughout the study and strategies were implemented to maintain consistent implementation of recruitment processes across sites.

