Costs: Total costs per person will be calculated by summing direct healthcare costs and indirect costs using a human capital approach for missed occupational activities. Sources of direct healthcare cost data: Intervention costs will include the PT salary and training needed to carry out the intervention. Costs for publicly funded healthcare services will be obtained from the Ontario Ministry of Health Schedule of Benefits. Medication costs will be obtained from the Ontario Drug Benefit formulary. Expenses related to health services funded by private insurance or out of pocket will be collected through self-report at all follow-up assessments. Other costs incurred by the participant related to their LBP are also being collected by self-report, including support or assistance for self-care, housework,

shopping, or transportation (e.g., to healthcare appointments). The total direct costs will be determined by multiplying the quantity of resource use by the corresponding unit cost, summing the total cost over each follow-up interval, and then calculating the mean cost at each follow-up time point, as well as an overall mean cost for the entire study period. *Indirect costs:* Non-healthcare costs will be limited to loss of productivity using a human capital approach. The mean provincial wage reported by Statistics Canada will be used to assign a monetary value to time lost from paid employment. The minimum wage value in Ontario and BC will be used to place a value on time lost by those who were retired and time lost from volunteer, homemaking, caregiving, or educational activities.

**Cost effectiveness:** We will conduct a cost-utility analysis from both societal (primary) and health payer (secondary) perspectives to meet the needs of all knowledge users. For both societal and health payer perspectives, we will estimate the incremental cost-per-QALY gained.

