#### **Patient health and experience outcomes**

For our patient health outcomes, we will use linear mixed models to estimate individual patient participant outcomes adjusting for clustering by primary care centre. Our primary outcome (RMDQ) with repeated measures at baseline and the 6-week, 3-, 6-, 9-, and 12-month follow-up time points will be analyzed using linear mixed regression (using *PROC MIXED* in SAS), estimated using restricted

maximum likelihood (REML) estimation and a Kenward-Rogers degrees of freedom correction to account for a small number of clusters. The model will include fixed effects for time, intervention group by time interaction, (omitting the group main effect to ensure baseline differences are constrained to zero), factors used in the covariate-constrained allocation procedure (rurality of the cluster, number of active patients) and other pre-specified covariates associated with LBP-related disability (patient participant age, sex, income, highest level of education achieved, duration of current episode of LBP, Functional Comorbidity Index score). The correlation in repeated measures on the same participant will be modeled using a suitable covariance structure, identified using information criteria (AIC/BIC). To account for clustering within practices, site will be modeled as a random effect. The intervention effect will be obtained as the adjusted least square mean difference between arms at 12 months, with 95% confidence intervals. Secondary comparisons will be obtained using least square mean differences at intermediate time points.

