#### Economic evaluation

We will estimate the cost-effectiveness of the PT-led care model from both a societal (primary) and health system payer (secondary) perspective to meet the needs of all knowledge users. The total costs will be determined by multiplying the quantity of resource use (or lost days) by the corresponding unit cost (or hourly wage), summing the total cost over each follow-up interval, and then calculating the mean cost at each follow-up time point, as well as an overall mean cost for the entire one-year study period. Results will be presented as aggregated and disaggregated costs. Utility data will be generated using EQ-5D-5L index values (ie. utility scores) from all follow-up assessment time points. We will estimate QALYs for every participant, using the area under the curve approach, assuming linear interpolation between the measurements. To accommodate the hierarchical structure of the data, we will use bivariate multilevel modeling to estimate the incremental cost-effectiveness ratio using a calculation of cost-per-QALY gained for PT-led primary care versus usual care and to estimate the incremental net benefit at various willingness to pay values. To account for clustering of study sites, as well as heterogeneity in costs and treatment effect across jurisdictions, we will model treatment group as

a fixed effect and the study site a random effect; adjusting for the same covariates as the primary analyses as fixed effects in our models. We will conduct a probabilistic sensitivity analysis using 10,000 Monte Carlo simulations to present the uncertainty in our cost-effectiveness estimates. Simulation results will be plotted on cost-effectiveness planes and we will generate cost-effectiveness acceptability curves to display the probability that the PT-led care model is cost-effective across a range of willingness to pay thresholds.

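### The economic model claims to account for differences between jurisdictions, but it fits one common arm effect without province, and publicly funded services and drugs at the BC sites have only Ontario price sources

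*Combined protocol and SAP*

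**What the plan says.** Under Economic evaluation, the bivariate multilevel model is meant to deal with clustering by site "as well as heterogeneity in costs and treatment effect across jurisdictions". To do this, treatment group is "a fixed effect and the study site a random effect; adjusting for the same covariates as the primary analyses". In the primary model (Patient health and experience outcomes), the cluster-level covariates are "rurality of the cluster, number of active patients"; the rest are patient characteristics. Province is not among them, although allocation was stratified by location (Allocation of Participating Primary Care Teams to Trial Groups). The planned subgroup analyses are by sex and by STarT Back class, with none by province.

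The sites are "14 in Ontario and 6 in British Columbia, Canada" (Recruitment). On prices, the Costs paragraph of Health System and Societal Outcomes says: "Costs for publicly funded healthcare services will be obtained from the Ontario Ministry of Health Schedule of Benefits". It adds: "Medication costs will be obtained from the Ontario Drug Benefit formulary". No BC source is named for either. Paid work time is valued at the provincial mean wage, and for unpaid time "The minimum wage value in Ontario and BC will be used". Private and out-of-pocket expenses are self-reported. The intervention cost includes the physiotherapist's salary, but the source of that salary is not given.

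**The concern.** The stated aim and the listed terms do not match. Whole sites are randomized, so arm is constant within a site, and a site random intercept can only move that site's mean. With one fixed arm coefficient and no province term, the effects on cost and on QALYs are each a single number for both provinces.

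The pricing makes the mismatch sharper. For list-priced care, no Ontario-BC price difference can enter the data, while lost time is valued by province. This matters most for the health payer perspective, where publicly funded items carry the weight and lost productivity does not.

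The trial is meant to inform health system decision makers. As worded, they would believe that the net-benefit result allows for an effect that differs by province. What they would receive is a blended effect, with BC public services and drugs valued at Ontario prices.

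**Working it through.** The plan gives no figure on this point, so there is none to reproduce. The check has three parts.

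**1. What the listed terms can estimate.** With 20 sites, 20 site indicators have rank 20. Adding arm leaves the rank at 20, and adding arm-by-site also leaves it at 20. A site's own treatment effect cannot be separated from its intercept. By contrast, the design with intercept, arm, province and arm-by-province has full rank (4 of 4), provided each province has sites in both arms.

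**2. What the planned model does with provincial differences.** Assumptions, not in the documents: 7 v 7 Ontario and 3 v 3 BC sites (inferred from 1:1 allocation stratified by location), 40 patients per site, site SD 100, patient SD 300, arbitrary cost units. With equal site sizes, least squares on site means is equivalent to the random-intercept model. The closed forms below were compared with a simulation of 20,000 replicates.

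- Variance of a site mean: 100² + 300²/40 = 10,000 + 2,250 = 12,250.
- No provincial difference: SE of the arm effect = √(12,250 × (1/10 + 1/10)) = 49.5 (simulated mean 48.7).
- Mean cost 400 higher in BC, same arm effect of -200: the added within-arm sum of squares is 2 × 10 × 0.7 × 0.3 × 400² = 672,000, and 672,000/18 = 37,333. SE = √(49,583 × 0.2) = 99.6 (simulated 98.8). Apparent site SD = √47,333 = 217.6 (simulated 217.3). The arm effect stays unbiased.
- Arm effect -400 in Ontario and +267 in BC, same usual-care cost: the pooled estimate is 0.7 × (-400) + 0.3 × 267 = -200. The added sum of squares, in the intervention arm only, is 10 × 0.7 × 0.3 × 666.7² = 933,333, and 933,333/18 = 51,852. SE = √(64,102 × 0.2) = 113.2 (simulated 112.8). Apparent site SD = √61,852 = 248.7 (simulated 249.0).

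Adding terms to the model gives (simulated values):

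| Scenario | Planned model | + province | + province and arm-by-province |
|---|---|---|---|
| Cost level differs by 400 | SE 98.8, site SD 217.3 | SE 48.7, site SD 99.7 | interaction about 0, site SD 99.7 |
| Effect differs (-400 / +267) | effect -200, SE 112.8, site SD 249.0 | effect -200, SE 88.5, site SD 193.8 | Ontario -401, BC -401 + 668 = +267, site SD 100.1 |

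Precision of the provincial estimates, relative to the overall arm effect:

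- Interaction: √(1/7 + 1/7 + 1/3 + 1/3) / √(1/10 + 1/10) = 0.976/0.447 = 2.2.
- BC effect alone: √(1/3 + 1/3) / 0.447 = 0.816/0.447 = 1.8.

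**3. Reach of the Ontario prices.** BC sites: 6/20 = 30%. Let BC unit prices differ from Ontario's by 10-20% (assumption), let Ontario-listed items be a share s of direct cost, and let sites be of equal size. The error is then s × 10-20% in BC direct cost and 0.30 × s × 10-20% in pooled direct cost.

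- s = 1 (upper limit): 10-20% in BC, 3-6% pooled.
- s = 0.5: 5-10% in BC, 1.5-3% pooled.

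These are errors in cost level. With both arms present in BC, a uniform price gap scales the BC cost difference on the listed items by the same 10-20%. It does not create a difference where none exists.

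**The case against.** The strongest reply is that accounting for heterogeneity does not promise provincial estimates. The random intercept takes up a gap in mean cost between provinces, and the arm effect stays unbiased. Even a differing effect leaves a trace in a larger site variance and a wider interval. A pooled average is a legitimate target, a single price set is a defensible costing choice, and disaggregated costs will be reported.

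Much of this stands. The cost half of the claim is met in a weak sense. The treatment-effect half is not: a wider interval neither identifies a provincial difference nor lets the effect vary. Nor is the single price set declared or justified as such, and the planned probabilistic sensitivity analysis is not said to vary prices by province.

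A reader might infer stronger points that the documents do not support:

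- That a cluster trial cannot address provincial effects at all. The limit lies in the listed terms; an arm-by-province term is estimable.
- That all direct costs carry Ontario prices. Only publicly funded services and medications do. Private and out-of-pocket costs are self-reported, and the province of the salary source is unstated.
- That provincial cost differences vanish before modelling. Resource quantities are multiplied by unit prices, so differences in use remain; only list-price differences are lost.

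**Conclusion.** The point holds in this limited form. The model as written yields one common arm effect and does not deliver the stated allowance for an effect that differs by jurisdiction. It handles a provincial difference in cost level only as noise: under the assumed variances, the SE rises from about 49 to 99, and a province term restores it. With provinces balanced across arms, that inflation is avoidable.

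On prices, 30% of sites have no own-province source for publicly funded services and drugs. The pooled direct-cost error would be at most about 3-6% if prices differ by 10-20%, and less as the share of listed items falls. That gap, the equal site sizes and the 3 v 3 split in BC are assumptions or inferences. The documents do not show that prices or effects actually differ between the provinces.

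This concerns the economic evaluation and leaves the RMDQ conclusion untouched. It is worth correcting before analysis, which the plan says starts only after data collection ends.

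**What to change.** 1. Add province as a fixed effect in both the cost and the QALY equations. It is the randomization stratum and costs one site-level degree of freedom.
2. Add an exploratory arm-by-province term and report incremental net benefit by province beside the pooled value, labelled descriptive because there are only about 3 BC sites per arm. Otherwise delete the claim to account for treatment-effect heterogeneity across jurisdictions.
3. Price BC participants' publicly funded services and medications from BC lists, at least as a scenario analysis. Otherwise state that Ontario prices are a deliberate common price set and justify it.
4. State the source and province of the physiotherapist salary.

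The cost is one more price list, two model terms in each equation, and provincial estimates that will be imprecise (SE about 1.8 times the overall SE for the BC effect and 2.2 times for the interaction). The change can be recorded by the plan's own amendment route, through the trial registry and the full trial publication.

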**Trial Status**

This trial was registered prospectively in January, 2020 at ClinicalTrials.gov (NCT04287413). Recruitment of primary care sites (clusters) was completed in June 2023 (after being delayed due to the COVID-19 Pandemic). Cluster randomization was performed in July 2023. Patient participant recruitment was initiated in October, 2023 and completed in November, 2024. Data collection is ongoing as of the submission of this protocol with data collection planned for completion by December 19, 2025. Data analysis will be carried out in accordance with this pre-specified analysis plan and will commence following the completion of data collection. No interim analyses have been conducted. Results are expected to be published in 2026.

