### **Frequency and Duration of Follow-Up:**

Patient characteristics and demographic information were collected at baseline. All patient-reported outcome measures are being collected at baseline, 6 weeks, and 3, 6, 9, and 12 months from the initial visit, with the primary comparison at 12 months. Patient satisfaction, global rating of change, adverse effects, and healthcare utilization are being collected at follow-up time points only. Patient adherence to PT recommendations is being collected at the 6-week follow-up.

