Pain intensity, health-related quality of life (EQ-5D-5L), PSEQ, PCS, TSK-11, and PHQ-2 outcomes will be analyzed as described for the primary outcome, adjusted for the same covariates. Patient satisfaction and global rating of change outcomes have no baseline measures, and will be analyzed using ordinal logistic regression with clusters as random effects, adjusting for the same covariates as described above. When individual items are missing from within any of the questionnaires, we will use simple mean imputation as suggested by Chavance. Serious adverse events will be presented descriptively by arm due to low expected counts. Any adverse events (yes/no) will be presented as incidence rates with confidence intervals and compared by calculating relative risks with confidence intervals from robust Poisson regression using GEE-type robust variance estimators (using *PROC GLIMMIX* with *EMPIRICAL* option in SAS) to account for clustering and using an exchangeable working correlation matrix. We will use empirical covariance (“sandwich”) bias-adjusted (residual-based) estimators and the Fay and Graubard correction to account for small number of clusters in all models comparing incidence rates. In the case of non-convergence or unstable estimates due to the small number of clusters, we would attempt to fit the model using an independent working correlation matrix. Other information related to non-serious adverse events (i.e., severity and duration) will be reported descriptively.

We have planned a secondary analysis, a responder analysis, to compare the proportion of participants who experience a meaningful improvement in disability (RMDQ) in the PT-led primary care model arm versus the usual care arm. We will define a meaningful improvement as an improvement of greater than or equal to 30% improvement on the RMDQ, corresponding to an established minimally important difference among people with LBP. We will calculate the proportion of participants who

experience a meaningful improvement in each arm and compare between groups using robust Poisson regression, with GEE-type robust variance estimators to account for clustering. We will use empirical covariance (“sandwich”) bias-adjusted (residual-based) estimators and the Fay and Graubard correction to account for small number of clusters.

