#### Healthcare utilization and missed occupational activity outcomes

For healthcare utilization and missed occupational activities outcomes, we will estimate the average effect at the patient level across the population (marginal models), accounting for clustering using GEE-type robust variance estimators and robust Poisson regression with an exchangeable working correlation matrix. All of the models generated for our healthcare utilization and missed occupational activities outcomes will include the same covariates as our analysis for patient health outcomes: age, sex, highest level of education achieved, income, duration of current episode of LBP, and Functional Comorbidity Index score (individual level), and primary care site rurality and number of active patients (cluster level). In the case of non-convergence or model instability, a possibility for any binary outcomes with very low or high event rates given our small number of clusters, we will attempt to model outcomes using an independence working correlation matrix. If we continue to experience issues with non-convergence or instability with alternate covariance structures, we will remove covariates, starting with duration of pain and income based on theoretical grounds and existing evidence on the strength of relationships between our covariates and our outcomes.

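### The cost/QALY model borrows a covariate list with no baseline outcome, so incremental QALYs are not adjusted for baseline EQ-5D-5L utility

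*Combined protocol and SAP*

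**What the plan says.** The economic evaluation section reduces each participant's utilities to one QALY by the area-under-the-curve method. It then models cost and QALY jointly, with treatment as a fixed effect and site as a random effect, "adjusting for the same covariates as the primary analyses as fixed effects in our models".

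The list it refers to is in the analysis section on patient health and experience outcomes. It holds the two site-level allocation factors (rurality, number of active patients) and "other pre-specified covariates associated with LBP-related disability". The section on healthcare utilization restates the patient-level part as "age, sex, highest level of education achieved, income, duration of current episode of LBP, and Functional Comorbidity Index score (individual level"). Neither place lists baseline RMDQ or baseline EQ-5D-5L.

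The primary model deals with baseline differently. Baseline RMDQ is one of the repeated responses, and the model is fitted "omitting the group main effect to ensure baseline differences are constrained to zero". The same section extends this to EQ-5D-5L as a health outcome: "health-related quality of life (EQ-5D-5L), PSEQ, PCS, TSK-11, and PHQ-2 outcomes will be analyzed as described for the primary outcome".

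Baseline utility is available: "All patient-reported outcome measures are being collected at baseline, 6 weeks, and 3, 6, 9, and 12 months from the initial visit". Table 1 agrees. For the economic analysis, however, the plan says "Utility data will be generated using EQ-5D-5L index values (ie. utility scores) from all follow-up assessment time points", and does not mention baseline.

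**The concern.** The covariate list is complete for the model it was written for, because that model handles baseline through its structure. Taken alone into a model with one total per person and a treatment main effect, it loses the baseline adjustment. There is no time-by-group term left to constrain, and nothing in the list replaces it. The same EQ-5D-5L index would then be baseline-adjusted as a health outcome and not adjusted as a QALY.

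What is at stake is the incremental QALY. It is the denominator of the cost-per-QALY ratio and feeds net benefit and the acceptability curves. Cost-effectiveness is part of the second research question.

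Two design features make a baseline utility difference plausible:

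- Only 20 sites were randomized, with allocation constrained on region, practice size and rurality but not on utility.
- Patients were enrolled after sites knew their arm: "Cluster randomization was performed in July 2023. Patient participant recruitment was initiated in October, 2023". The plan takes sensible steps against recruitment bias, but any imbalance need not be chance alone.

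**Working it through.** **The plan's own figure.** No power or precision is stated for QALYs. The nearest benchmark is the RMDQ calculation under Sample Size and Power Calculations: difference 2.5, SD 5.7, ICC 0.1, cluster autocorrelation 0.5, individual autocorrelation 0.6, 18 clusters of 63, two-sided 0.05.

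- Design effect = 1 + 62 × 0.1 = 7.2.
- r = (63 × 0.1 × 0.5 + 0.9 × 0.6)/7.2 = 0.5125.
- With baseline adjustment: variance of the difference = 2 × 5.7² × 7.2 × (1 − 0.5125²)/(9 × 63) = 0.608, SE 0.780, power 89.4% by the normal approximation. This reproduces the stated 90%.
- Without it: variance 0.825, SE 0.908, power 78.6%.

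On the plan's own inputs, baseline adjustment is therefore worth about 11 points of power for RMDQ.

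**Weight of baseline in the QALY.** Linear interpolation over 0, 6 weeks and 3, 6, 9 and 12 months gives weights 0.058, 0.125, 0.192, 0.250, 0.250 and 0.125. Starting the curve at baseline therefore does not adjust for baseline. An imbalance of 0.03 adds only 0.0017 QALY mechanically; the larger part arises because later utilities correlate with baseline.

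**Size of a chance imbalance.** Utility SD and ICC are assumptions. With 10 sites of 78 per arm, SE = √[2 × SD² × (1 + 77 × ICC)/780].

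| SD | ICC | SE of baseline difference |
|---|---|---|
| 0.15 | 0.02 | 0.0121 |
| 0.20 | 0.05 | 0.0223 |
| 0.25 | 0.10 | 0.0373 |

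**Carry-over into incremental QALYs.** The expected fraction is 0.058 + 0.942 × c, where c is the assumed baseline-to-follow-up correlation. For c = 0.4, 0.5 and 0.6 this is 0.435, 0.529 and 0.623. A one-SE imbalance, before other covariates, shifts incremental QALYs by 0.0121 × 0.435 = 0.005 up to 0.0373 × 0.623 = 0.023.

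**Loss of precision.** Borrow r = 0.5125 for utility and assume that follow-up utilities correlate with each other at 0.5125 to 0.80. The SE ratio (baseline omitted to baseline included) is 1/√(1 − ρ²), where ρ is the correlation of baseline utility with the QALY total. If the listed covariates explain a share a of utility variance, each correlation becomes (correlation − a)/(1 − a).

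| Share explained by covariates | Carry-over | SE ratio, follow-up correlation 0.5125 | SE ratio, follow-up correlation 0.80 |
|---|---|---|---|
| 0 | 0.54 | 1.387 (ρ = 0.693) | 1.252 (ρ = 0.601) |
| 20% | 0.426 | 1.245 | 1.146 |
| 30% | 0.344 | 1.169 | 1.093 |

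**Check by simulation.** In 3,000 simulated trials (20 sites of 78, no treatment effect, SD 0.20, ICC 0.02-0.10, random site intercept, no other covariates):

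- the mean unadjusted effect was about 0.000, so there is no bias over allocations;
- the slope of the unadjusted incremental QALY on the observed imbalance was 0.53-0.56, falling to −0.06 to −0.09 once participant baseline utility was added;
- the SE ratio was 1.22-1.41.

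**The case against.** The strongest reply is that the plan under-specifies rather than excludes. Its primary analysis does account for baseline, the sample size rests on a baseline-adjusted ANCOVA, and an analyst might read the cross-reference as carrying the equivalent adjustment. That is possible, but the sentence borrows covariates, and baseline is not a covariate in the primary model. If the adjustment is intended, the remedy is still to write it down.

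Other points against:

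- **Loss of precision and conditional bias are one variance component.** This is right under sound randomization. The intervals would be wider, not invalid.
- **The listed covariates give some protection.** Also right. Age, comorbidity, episode duration and the rest absorb part of any imbalance, so the 9-25% range describes the planned model better than 25-39%. No imbalance has been reported, and allocation was disclosed only after consent and baseline data. If recruitment did differ by arm, adding baseline utility would correct only the part that utility captures.
- **The magnitudes are assumed.** True: no utility SD, ICC or correlation is in the documents.
- **The follow-up wording is minor.** True. Interpolating between measurements can be read to include baseline, so this point adds no weight.

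These objections reduce the size of the problem. None of them puts baseline utility into the economic model.

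**Conclusion.** The concern holds. No section enters the baseline EQ-5D-5L index in the cost/QALY model, and the primary model's baseline constraint cannot apply to a single QALY total. The result is a less precise incremental QALY that moves with whatever baseline utility difference is observed.

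The most relevant estimate is a standard error about 9-25% larger and a carry-over of about 34-43% of a baseline difference. This assumes that utility behaves like RMDQ over time and that the listed covariates explain 20-30% of its variance. Without that absorption the figures are 25-39% and, over assumed correlations of 0.4-0.6, about 43-62%.

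The effect is confined to the economic evaluation. The RMDQ analysis and EQ-5D-5L as a health outcome already account for baseline. The change should be made, but nothing in the primary conclusion depends on it.

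**What to change.** Before analysis begins, amend the economic evaluation section in three ways:

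- Add each participant's baseline EQ-5D-5L index as a fixed covariate in the QALY equation of the bivariate multilevel model. Its site mean could be added as well, but is optional.
- State that the area under the curve runs from the baseline utility to 12 months.
- State how a missing baseline index will be handled.

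The cost is a few lines of text and one covariate that is already collected. The Trial Status section says analysis starts only after data collection ends, and the section on protocol and analysis plan amendments gives the route: the registry entry and the trial report. Making the change now also avoids the appearance of choosing the adjustment after seeing an imbalance.
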